Sham treatment will include 10 seconds of ramp in to 20 seconds of 10 Hz tACS with a ramp out of 10 seconds for a total of 40 seconds of stimulation. The rationale for this choice of an active sham is that it may enhance success of patient blinding by mimicking skin sensations associated with tACS. 10 Hz tACS will have a 10 second ramp in and ramp out with 40-minutes of stimulation for a total of 1220 seconds of stimulation, daily for five days. Stimulation waveform is a sine-wave with a peak-to-peak amplitude of 2 mA. In each treatment regimen, participants will stay in a relaxed and controlled state by watching a nature movie such as "ReefScape" during stimulation. The maintenance regimen will provide one 40-minute stimulation per week.

Eligible participants who complete this clinical trial will have a total of 15 to 18 visits; an initial screening session, a 2nd screening session, (if needed) 2 more follow up screening sessions, 5 days of daily stimulation sessions, 1 sMRI visit, and 8 weekly maintenance stimulation sessions. The initial phone screening session will take approximately 2 hours, and each follow up screening session will take approximately 30 minutes each. The first day of stimulation will take approximately 4 hours and days 2 through 4 of stimulation will take 1.5 hours each. The last day of stimulation will take about 4 hours. sMRI visits will last approximately 2 hours. Maintenance stimulation sessions weeks 1 and 3 will be approximately 3 hours each, maintenance weeks 2, 4, 5, 6, and 7 will be approximately 2 hours each, and the final maintenance stimulation session week 8 will be approximately 5 hours. We estimate that total participant participation duration will be approximately 35 to 39 hours. A small subset of participants will be recruited for a 12 week observational case study to assess the feasibility of long-term at-home maintenance treatment.

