## 7 STUDY PROCEDURES/EVALUATIONS

### 7.1 STUDY SPECIFIC PROCEDURES

During the initial session, researchers will collect demographics. Participant demographics include medical history and medication history. This information is used to confirm inclusion criteria and that no current alcohol and drug abuses or disorder exist.

Several clinical evaluations will be used throughout this study. These assessments are listed below and can be found in the attached documents.

- i. The Structured Clinical Interview for DSM-IV Axis I Disorders (SCID-I) is a semi-structured interview used to diagnosis major Axis I disorders. For this study, the SCID-I (First et al. 2004) will be administered at baseline in order to confirm a diagnosis of Schizophrenia or Schizoaffective Disorder.
- ii. The Columbia Suicide Severity Rating Scale (C-SSRS) is a semi-structured interview designed to assess suicidality. The assessment will be administered at baseline, the first day of stimulation, the fourth maintenance stimulation session, and the final maintenance stimulation session.
- iii. The Auditory Hallucination Rating Scale (AHSRS) is a structured interview, designed to assess different aspects of patient's auditory hallucinations. This assessment has 11 items and is rated on a scale of 0 – 4 based on the responses given by the patient. The AHSRS will be administered at the baseline visit, each screening session, the first day of stimulation, the last day of stimulation, and at each of the maintenance stimulation sessions.
- iv. The Positive and Negative Syndrome Scale (PANSS) is a structured interview used to assess the symptom severity of patients diagnosed with schizophrenia. The PANSS (Kay et al. 1987) focuses on the positive and negative syndromes and their general severity. This scale will be administered at the

first day of stimulation, the last day of stimulation and at the final maintenance stimulation session (week 8).

v. The Brief Assessment of Cognition in Schizophrenia (BACS) will be administered at the first day of stimulation, the last day of stimulation and at the final maintenance stimulation session (week 8) in order to monitor changes in participant cognition. This validated assessment (Keefe et al. 2004, Keefe et al. 2006) contains 6 tests that focus on verbal memory and learning, working memory, motor functioning, attention/processing speed, verbal fluency and reasoning and problem solving.

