## 10 STATISTICAL CONSIDERATIONS

### 10.1 STUDY HYPOTHESES

We hypothesize that

- (1) Daily tACS stimulation for 5 days reduces auditory hallucination symptoms as measured by the AHRS, PANSS and BACS survey instruments, and that
- (2) weekly tACS stimulation during a follow-up maintenance regimen extends the duration of that clinical benefits as measured by the AHRS, PANSS and BACS.

We hypothesize that

- (1) baseline impairment in EEG oscillations and connectivity predicts treatment success, and that
- (2) changes in these markers are correlated with improvement of clinical symptom presentation as measured by the AHRS, PANSS, and BACS.

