For AHRS,  $Y_{ij}(t_0)$  is the baseline score from the  $i$ -th participant in the  $j$ -th treatment sequence ( $j = SS, SA, AS, AA$ ). The primary analyses will focus a linear mixed-effects model for the change from baseline on occasion  $t$ ,  $\Delta Y_{ij}(t) = Y_{ij}(t) - Y_{ij}(t_0)$ , conditional on the following explanatory variables: assigned treatment regimen, treatment stage (initial daily stimulation vs maintenance weekly stimulation), and baseline score  $Y_{ij}(t_0)$  as a covariate.

$$[\Delta Y_{ij}(t) | \mathbf{X}, Y_{ij}(t_0)] = \mu_S X_1 + \mu_A X_2 + \tau_S X_3 + \tau_A X_4 + \lambda X_5 + \beta (Y_{ij}(t_0) - \bar{Y}(t_0)) + \varepsilon_i + \varepsilon_{ij}(t)$$

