Here,  $\bar{Y}(t_0)$  is the average of all baseline values. The expected value is shown in **Table 1** below. The fitted model will be used to tabulate statistical estimates (all with 95% confidence intervals) of the population parameters of interest: variance components, intra-class correlation, the direct effect of treatment ( $\mu_S - \mu_A$ ) in period 1, treatment-specific period effects ( $\tau_A, \tau_S$ ), and a longer-term treatment effect ( $\lambda$ ) that carries over from period 1 into period 2. Parameters  $\tau_A$  and  $\tau_S$  represent both the period-by-treatment interaction and also the 'period effect' ( $\tau_A + \tau_S$ ). In a 2-sequence crossover design, parameters  $\tau_A, \tau_S$  and  $\lambda$  would be aliased together; whereas, in the 4-sequence design they are not aliased. For the main analysis we assume carryover effect  $\lambda$  vanishes in the later weeks of the maintenance regimen in period 2; that is, effects of any treatments in period 1 have washed out by the end of the maintenance regimen. (That would not be the case if treatment A in period 1 cured the patient.) The sensitivity of the main results to this assumption will be investigated in auxiliary sensitivity analyses. In this model, the direct treatment effect in period 1 is  $(\mu_S - \mu_A)$  while the direct treatment effect in period 2 is  $((\mu_S + \tau_S) - (\mu_A + \tau_A))$ . We conjecture that  $\tau_S \approx 0$  and that  $\tau_A$  has a small negative value owing to weekly stimulation having a somewhat smaller effect than daily stimulation. The magnitude of  $\tau_S$  is of interest because it represents the efficacy of montly stimulation relative to daily stimulation. The magnitude of  $\lambda$  is of interest because it represents impact of treatment that endures into (at least) the beginning of the maintenance regimen.

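### Section 10.2 gives the wrong reading of its own period parameters: τ_S is the sham period effect, not the efficacy of maintenance relative to daily stimulation, and the predicted sign of τ_A contradicts the reason given for it

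*Combined protocol and SAP*

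**What the plan says.** All of this is in the Combined protocol and SAP.

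- **Outcome.** Section 10.2 uses a "linear mixed-effects model for the change from baseline on occasion" t, that is, ΔY(t) = Y(t) − Y(t0).
- **Parameters.** τ_A and τ_S are introduced as "treatment-specific period effects". In Table 1 (which prints m for μ), the mean is μ_S or μ_A in period 1. In period 2 it is μ_S + τ_S under sham and μ_A + τ_A under active stimulation, plus λ at t2 to t5 for those who had active treatment first.
- **Contrasts.** The period 1 effect is (μ_S − μ_A), and "the direct treatment effect in period 2 is" ((μ_S + τ_S) − (μ_A + τ_A)). The primary null sets both (μ_S − μ_A) and (τ_S − τ_A) to zero, using t1 and t9 with λ = 0.
- **Reading of the parameters.** The plan conjectures that τ_S is about 0 and that τ_A "has a small negative value owing to weekly stimulation having a somewhat smaller effect than daily stimulation". It then says that the magnitude of τ_S "represents the efficacy of montly stimulation relative to daily stimulation".
- **Schedule.** Section 4.2: "The maintenance regimen will provide one 40-minute stimulation per week".

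**The concern.** Two statements in the same paragraph conflict with the model that they explain. The first attaches relative efficacy to a parameter that describes only sham. The second gives τ_A a sign that means the opposite of the reason offered for it.

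Section 10.2 puts the weight on estimates and intervals rather than p-values, so the stated meaning of each parameter matters. An analyst who followed the text would report sham drift as the efficacy of the maintenance schedule. The same analyst would take a negative τ_A, which is further improvement, as confirming a weaker effect. The joint F-test has no direction, so explaining a rejection that comes from its (τ_S − τ_A) component depends on this reading. Section 10.2 also expects the same approach to serve for PANSS, BACS and EEG alpha power.

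**Working it through.** **Inputs**

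- Direction: section 7.1 describes the AHRS as 11 items scored 0 to 4, and section 10.1 hypothesises that "Daily tACS stimulation for 5 days reduces auditory hallucination symptoms as measured by the AHRS". Lower is better, so benefit is a negative ΔY.
- Pilot mean changes (Table 2): sham -2.29, active -3.75.
- Conditional variance components (Table 2): inter-subject 4.98 (2.66 to 12.35), intra-subject 0.55 (0.30 to 1.37).
- Design: 40 participants, 10 per sequence, occasions t1 and t9, λ = 0.

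**1. The plan's own power figure.** Section 10.3 states 90% [50%, 99%] for (μ_S − μ_A) = 1.18 at α = 0.025. With the four sequences balanced, the effects in periods 1 and 2 are estimated independently, each with variance (4/40) × (5.53² − 4.98²)/5.53 = 0.1 × 5.7805/5.53 = 0.1045, so SE = 0.323. A non-central F with 1 and 37 df gives 90.0%. The interval limits of the variances give 99.4% and 49.7%. The figure is reproduced, which confirms the Table 1 parameterisation and that a positive (μ_S − μ_A) means benefit.

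**2. What each parameter measures**

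- Period 1 effect: μ_S − μ_A.
- Period 2 effect: (μ_S − μ_A) + (τ_S − τ_A).
- Change in effect, period 2 minus period 1: **τ_S − τ_A**.

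With λ = 0, τ_S alone is the period 2 sham mean minus the period 1 sham mean. Because the plan conjectures τ_S near 0, its reading would make relative efficacy about zero by assumption, whatever τ_A is.

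**3. Sign of τ_A.** The pilot difference is -2.29 − (-3.75) = 1.46. With τ_S = 0, the period 2 effect is 1.46 − τ_A.

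| Share of daily effect kept (assumed) | Period 2 effect | τ_A required |
|---|---|---|
| 90% | 1.314 | +0.146 |
| 75% | 1.095 | +0.365 |
| 50% | 0.73 | +0.73 |
| 25% | 0.365 | +1.095 |

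In the other direction, τ_A = -0.25 gives 1.71 (117% of the daily effect) and τ_A = -0.5 gives 1.96 (134%). Any loss of effect needs a positive τ_A. More generally, it needs τ_A > τ_S.

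**4. What the estimates would show.** In 2,000 simulated trials with these variances, τ_S = 0 and half the effect kept (τ_A = +0.73), the mean estimates were -0.004 for τ_S and +0.733 for τ_A. The estimate of τ_A was positive in 99.5% of trials. The estimate of τ_S lay within ±0.5 in 92.6%. Reading τ_S would usually suggest no difference between schedules although half the effect had gone.

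**5. Precision**

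- Var(τ_S − τ_A) = 2 × 0.1045 = 0.209, so SE = 0.46 and the 95% half-width is about 1.96 × 0.457 = 0.90.
- Var(τ_S) = Var(τ_A) = 2 × 0.55/40 + 0.209/4 = 0.0275 + 0.0523 = 0.080, so SE = 0.28 and the half-width is about 0.55.

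Reporting a single τ in place of the contrast would therefore also overstate precision.

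**6. Other scales.** Section 8.6 treats a fall in cognitive scores as a worsening. For BACS, benefit is a positive change, so a weaker weekly effect would mean a negative τ_A.

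**The case against.** The strongest reply is that no computation uses either sentence. The same paragraph gives both direct effects correctly, section 10.2 names them as the focus with confidence intervals, and (τ_S − τ_A) is already in the primary null. A reader who saw both effects side by side would notice a halved weekly effect. All of that stands. A reader might infer from the two sentences that the primary analysis is invalid or will give a wrong answer; the documents do not support that.

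The subscript may also be a slip, in writing or typesetting, for τ_A, since the sentence about weekly and daily stimulation concerns τ_A. That is plausible, but putting τ_A there leaves the sign conflict and still takes no account of sham drift.

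A reader might also infer that comparing weekly with daily stimulation is the declared purpose of maintenance. The protocol summary and sections 3 and 10.1 give a different one, to prolong the benefit of the first week. The weekly-versus-daily comparison is called of interest only in the disputed paragraph.

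Finally, (τ_S − τ_A) is not a pure effect of frequency. It compares t1, after five daily sessions, with t9, after eight further weekly ones, and half of those on active maintenance also had active treatment in week 1. If λ is not zero at t9, carryover in the active-then-sham sequence enters the sham period 2 mean. These limits stand and belong in the text.

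**Conclusion.** Both misstatements follow from the plan's own definitions, and no sign convention in the document removes the second. They affect the stated reading of the daily-versus-maintenance comparison, and so the direction attached to the (τ_S − τ_A) component of the primary null. They do not affect the model, the F-test, the two named contrasts or the power figures.

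The sizes are illustrations. They rest on a pilot difference of 1.46 from 7 and 8 patients, τ_S = 0, λ = 0, all 40 participants analysed, and assumed shares of effect kept. The plan calls its value small, so the 50% row shows what a misreading could hide and is not a forecast. The sign conclusion holds at any size of loss. The point should be corrected before analysis.

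**What to change.** In the Aim 1 text of section 10.2:

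1. State that τ_S estimates the sham period effect.
2. State that the change in direct treatment effect from the daily week to weekly maintenance is (τ_S − τ_A), reported with its 95% CI. For AHRS a negative value means a smaller effect in maintenance. Add that this assumes λ = 0 at t9 and also reflects elapsed time, number of sessions and prior exposure.
3. Bring the frequency word into line with the weekly maintenance described in section 4.2 and in the neighbouring sentence.
4. Make the sign of the τ_A conjecture agree with its reason: positive for AHRS if weekly stimulation is expected to be weaker and τ_S is about 0. Note that the sign reverses for scales such as BACS where higher is better.

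The cost is a few sentences and one more reported contrast from the model already planned. No data, sample size or test changes.

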**Table 1. Conditional expected value of change from baseline evaluated at the average baseline value**

		Treatment Sequence			
		SS	SA	AS	AA
Period 1	$t_1$	$m_S$	$m_S$	$m_A$	$m_A$
	$t_2$	$m_S + \tau_S$	$m_A + \tau_A$	$m_S + \tau_S + \lambda$	$m_A + \tau_A + \lambda$
	$t_3$	$m_S + \tau_S$	$m_A + \tau_A$	$m_S + \tau_S + \lambda$	$m_A + \tau_A + \lambda$
	$t_4$	$m_S + \tau_S$	$m_A + \tau_A$	$m_S + \tau_S + \lambda$	$m_A + \tau_A + \lambda$
	$t_5$	$m_S + \tau_S$	$m_A + \tau_A$	$m_S + \tau_S + \lambda$	$m_A + \tau_A + \lambda$
	$t_6$	$m_S + \tau_S$	$m_A + \tau_A$	$m_S + \tau_S$	$m_A + \tau_A$
	$t_7$	$m_S + \tau_S$	$m_A + \tau_A$	$m_S + \tau_S$	$m_A + \tau_A$
	$t_8$	$m_S + \tau_S$	$m_A + \tau_A$	$m_S + \tau_S$	$m_A + \tau_A$
	$t_9$	$m_S + \tau_S$	$m_A + \tau_A$	$m_S + \tau_S$	$m_A + \tau_A$

For the primary analysis, the above model will be fitted using only AHRS scores at  $t \in \{t_1, t_9\}$  assuming  $\lambda=0$ :

$$E[\Delta Y_{ij}(t) | \mathbf{X}, Y_{ij}(t_0)] = \mu_S X_1 + \mu_A X_2 + \tau_S X_3 + \tau_A X_4 + \beta (Y_{ij}(t_0) - \bar{Y}(t_0))$$

The set of sensitivity analyses will include fitting the model using AHRS scores at  $t \in \{t_1, t_6, t_7, t_8, t_9\}$  (with  $\lambda=0$ ), which is anticipated to provide more precision and power for analysis of the treatment effects.

The analyses will focus on the point estimates and confidence interval estimates of the parameters of interest; for example,  $(\mu_S - \mu_A)$  and  $((\mu_S + \tau_S) - (\mu_A + \tau_A))$ . The data and the fitted model will be visualized via graphical figures. The fitted model using only AHRS scores at  $t \in \{t_1, t_9\}$  will be used to test the primary null hypothesis,  $H_0: "(\mu_S - \mu_A) = 0 \text{ and } (\tau_S - \tau_A) = 0"$ , using an F-test of size  $\alpha = 0.05$ .

To explore carryover of treatment effects, the model

$$E[\Delta Y_{ij}(t) | \underline{X}, Y_{ij}(t_0)] = \mu_S X_1 + \mu_A X_2 + \tau_S X_3 + \tau_A X_4 + \lambda X_5 + \beta (Y_{ij}(t_0) - \bar{Y}(t_0))$$

will be fitted using AHRS scores recorded on occasions  $t \in \{t_1, t_2, t_3, t_4, t_5, t_6, t_7, t_8, t_9\}$ .

Sensitivity analyses will be used to evaluate the robustness of the main results to reasonable perturbations of the methods and assumptions used. This set of analyses will examine goodness of fit diagnostics for the linear model, and will include modified versions of the main analyses.

**Plans for Aim 2.** *Evaluate the relative efficacy of the tACS treatment regimen and subsequent maintenance regimen in terms of changes in the mean levels of the PANSS score and the BACS score.*

We anticipate that the strategy and methods used for the analyses of AHRS scores in Aim 1 will also be appropriate for the analysis of PANSS and BACS scores for Aim 2.

**Plans for Aim 3.** *Evaluate the effects of the tACS treatment regimen and subsequent maintenance regimen in terms of changes in EEG alpha frequency power levels.*

We anticipate that the strategy and methods used for the analyses for Aim 1 will also be appropriate for the analyses in Aim 3 of changes in alpha band power calculated from EEG recordings. Graphical descriptive statistical methods will be used to visualize and summarize the temporal trajectories of the scores and alpha band power. Scores of clinical assessments and EEG recordings at other occasions of the maintenance sessions may be explored for the purpose of generating hypotheses.

**Plans for early discontinuation:** In the event of a participant discontinuing participation prior to completion of the study sessions, the participant's data set will not be included in analysis. Only completed data sets will be included in analysis.

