## SCHEMATIC OF STUDY DESIGN

At enrollment, the 40 eligible enrollees will be allocated by randomization to four treatment-sequence groups: tACS-tACS, tACS-sham, sham-sham, sham-tACS) (10 participants per sequence). The randomization will be stratified by sex.

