## 2.2 RATIONALE

Here, we propose a new innovative approach driven by rational design where we use non-invasive brain stimulation to directly target the circuit-level pathology of auditory hallucinations. Specifically, we will evaluate simultaneous tACS (10 Hz) to enhance synchronization between frontal and temporo-parietal areas of the left hemisphere. Such use of tACS to enhance synchronization has recently been introduced as a successful modulator of long-range synchrony mediating working memory (Polania, Nitsche et al. 2012). Additionally, we will use EEG data to develop a novel biomarker to show that decreases in auditory hallucinations are predicted by an increase in effective and functional connectivity between key brain regions. In the EEG analysis, we will also employ source localization techniques to estimate the spatiotemporal dynamics of neuronal currents in the brain. In this step, we can minimize estimation errors of the locations and strengths of the current sources in the brain by measuring individual locations of scalp electrodes and using structural magnetic resonance imaging (sMRI). Because the source localization techniques can be problematic, small errors in a source modeling step can lead to larger errors in brain activity analysis. Anatomical brain structure and electrode location for each participant is necessary components to get reliable and precise current sources in the brain. Ultimately, our goal is to treat patients based on demonstrable changes in brain activity, rather than on symptoms themselves. The proposed research is innovative because it employs a new form of non-invasive brain stimulation, tACS, which targets underlying functional neuropathology to treat medication refractory auditory hallucinations in schizophrenia. Additionally, we are developing novel EEG biomarkers as markers for treatment response. We recently completed a pilot clinical trial examining the efficacy of tACS compared to tDCS and sham for treating auditory hallucinations in patients with schizophrenia or schizoaffective disorder. Results from this study were negative with a strong placebo effect, however we found that tACS and sham showed lasting significant improvement of auditory hallucinations vs tDCS. Data collected in this study will be used to further understand the effect of tACS on auditory hallucinations and sustaining effects with maintenance sessions weekly for 2 months after the initial 5 days of stimulation.

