### 10.3 SAMPLE SIZE CONSIDERATIONS

It is difficult to recruit a large number of patients diagnosed with schizophrenia with persistent auditory hallucinations to participate in a single site extensive study. However, based on our recent experience recruiting for patients with these symptoms, we expect that we can successfully recruit 40 subjects from this population.

We evaluated the performance characteristics of the study design and analysis strategy under the assumption that only 40 subjects will be available. To do this we used information from a previous randomized study conducted in this lab (IRB 14-3285). That study obtained baseline AHRS scores ( $Y_0$ ) and post-treatment AHRS scores ( $Y_1$ ) from participants sampled from our target population using the same methods and inclusion/exclusion criteria.

**Table 2** lists information obtained: 7 patients received sham treatment (**S**), 8 received 10Hz tACS treatment (**A**).

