Based on **Table 2** estimates for AHRS, we anticipate that 20 participants per regimen in period 1 will provide a margin of error of about 1.0 AHRS unit for regimen-specific estimates of mean change from baseline; i.e., we anticipate a 95% C.I. of the form [mean change  $\pm$  1.0] for each regimen.

For the primary analysis, the model will be fitted using only AHRS scores at  $t \in \{t_1, t_0\}$ :

$$E[\Delta Y_{ij}(t) | X, Y_{ij}(t_0)] = \mu_S X_1 + \mu_A X_2 + \tau_S X_3 + \tau_A X_4 + \beta (Y_{ij}(t_0) - \bar{Y}(t_0))$$

We will test  $H_0: "(\mu_S - \mu_A) = 0 \text{ and } (\tau_S - \tau_A) = 0"$ , using an F-test of size  $\alpha = 0.05$ . However, for purposes of the analysis of anticipated power, we considered a close surrogate: testing  $H_0: "(\mu_S - \mu_A) = 0"$  and  $H_0: "(\tau_S - \tau_A) = 0"$  separately using F-tests each of size  $\alpha = 0.025$ . In **Figure 2**, power curves are for the test of  $H_0: "(\mu_S - \mu_A) = 0"$ .

The curves are based on the point-estimates and 95% C.I. estimates of intra-subject and inter-subject variance components expressed here as standard deviations (by taking square roots) which are in turn based on the data in Table 2 and based on a conjectured underlying correlation of 0.90 between  $t_0$  and  $t_1$ .

[figure not shown]
[figure not shown]
The probability ('power') of drawing a sample that yields a p-value  $< \alpha = 0.025$  is a function of the unknown magnitude of the treatment effect ( $\mu_S - \mu_A$ ) in the target population. In **Figure 2**, for example, if our conjectures and assumptions are true and in truth  $(\mu_S - \mu_A) = 1.18$  AHRS units, the likelihood of rejecting  $H_0: (\mu_S - \mu_A) = 0$ " is estimated to be 90% with C.I. [50%, 99%]. For comparison, **Figure 1** provides power curves for a test of  $H_0: (\mu_S - \mu_A) = 0$ " based on only the data from period 1 --an approach that does not take advantage of the crossover design.

**Figure 3** provides similar information for test of  $H_0: (\mu_S - \mu_A) = 0$ " based on AHRS scores recorded on occasions  $t \in \{t_1, t_6, t_7, t_8, t_9\}$  assuming carryover effect  $\lambda$  has vanished before  $t_6$ . Inclusion of the carryover effect in the model can reduce precision and power for the test of treatment effects.

When exploring carryover effects using scores from occasions  $t \in \{t_1, t_2, t_6, t_7, t_8, t_9\}$  to fit

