$$E[\Delta Y_{ij}(t) | X, Y_{ij}(t_0)] = \mu_S X_1 + \mu_A X_2 + \tau_S X_3 + \tau_A X_4 + \lambda X_5 + \beta (Y_{ij}(t_0) - \bar{Y}(t_0)),$$

the power curves in **Figure 4** indicate anticipated power levels for a test of  $H_0: (\mu_S - \mu_A) = 0$ " when it is assumed that carryover impacts the score at  $t_2$  but not the scores at  $t_6, t_7, t_8$  and  $t_9$ .

It is anticipated that some participants will have incomplete data. **Figures 5, 6, 7 and 8** indicate the performance of the test procedures when the sample size is reduced to 30 participants. (Compare to Figures 1, 2, 3 and 4).

**Figures 1 - 8** were computed using the ability of SAS PROC MIXED to calculate the non-centrality parameter of the distribution of the F-statistic for a completely specified linear mixed-effects model. The resulting power-curve estimates are conjectures based on 1) previous data from only 15 subjects, 2) assumptions about the appropriate model for the data, 3) an assumption that the variance components have the same magnitudes for treatments S and A, and 4) an assumption that the correlation coefficient for the model's compound-symmetry covariance structure is 0.90.

In summary, based on considerations of anticipated precision of estimators, anticipated power levels of test procedures, anticipated availability of research subjects, and stage of this line of research, we anticipate the study is likely to achieve its specific aims; i.e., there is low risk the study will be uninformative and inconclusive.

The follow-up case study will be used to assess feasibility of long-term maintenance. The sample size is low as we do not intend to perform statistical analysis on outcomes. This observational study will be used to inform future, large-scale studies evaluating treatment efficacy of this intervention.

Figure 5 EY\_1

[figure not shown]

Figure 6 EY\_1\_9

[figure not shown]

Figure 7 EY\_1\_6789

[figure not shown]
[figure not shown]

Figure 8 EY\_1\_2\_6789

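### The exploratory carryover model has no week effect, so a change shared by all groups between early and late maintenance is estimated as carryover of active tACS

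*Combined protocol and SAP*

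**What the plan says.** Section 10.2 (Plans for Aim 1) models change from baseline in AHRS with means μS and μA, maintenance shifts τS and τA, a carryover term λ, the baseline score and a random participant effect. In Table 1, λ is added only at t2–t5 and only in AS and AA. Every other maintenance cell is constant over time for a given regimen, so SS and SA each have one mean from t2 to t9.

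The carryover fit is introduced with "To explore carryover of treatment effects, the model" and uses t1–t9. Section 10.3 describes the same exploration on a different set, t1, t2 and t6–t9, with carryover at t2 only, and bases Figure 4 on it.

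λ is listed among the parameters to be tabulated with 95% confidence intervals. Its size is said to be of interest "because it represents impact of treatment that endures into (at least) the beginning of the maintenance regimen". The one test given a size (an F-test at 0.05) uses t1 and t9 with λ set to zero. A further sensitivity fit uses t1 and t6–t9, also with λ = 0.

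**The concern.** Nothing in the carryover model varies by week except λ. τS and τA absorb a constant shift over the whole of maintenance, but λ is the only term that can represent a difference between early and late maintenance, and it exists only in AS and AA. If scores in all four groups move between t2–t5 and t6–t9, for any reason unrelated to treatment, the movement in AS and AA is read as carryover. SS and SA are the randomised controls for exactly this movement, but the model fixes their change at zero and makes no use of it.

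At stake is the reading of λ as treatment impact that lasts into maintenance, which bears on the trial's second hypothesis (duration of benefit). The estimate of μS − μA from the same fit is at stake too, and that is the contrast for which Figure 4 gives power. Section 10.2 puts its emphasis on estimates and intervals, so a displaced interval matters even without a formal test.

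**Working it through.** **Inputs from the documents**
- 40 participants (Section 10.3: "under the assumption that only 40 subjects will be available"), with "10 participants per sequence" (schematic of study design).
- Table 2: inter-subject variance 4.98 and intra-subject variance 0.55, both conditional on baseline.
- Alternative from the same table: σ²(1 − ρ) = 29.10 × 0.10 = 2.91, which equals 5.82/2. This leaves 5.53 − 2.91 = 2.62 between subjects.

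**Input assumed.** A linear drift of 0.1 AHRS unit per week from t2 to t9 in every group, with no treatment or carryover effect. The documents give no such figure, so 0.05 and zero are shown as well.

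**Step 1: reproduce the plan's power.** For the t1/t9 fit with 4.98/0.55, generalised least squares gives a standard error of 0.323 for μS − μA. At a true difference of 1.18, a size-0.025 F-test (1 and 37 df) has power 90.0%. Table 2's upper and lower variance limits give 49.7% and 99.4%. Section 10.3 states 90% [50%, 99%], so the model and variances match the plan's.

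**Step 2: bias of λ by hand.** The drift at t2–t9 is 0, 0.1, …, 0.7. The early mean (t2–t5) is 0.15 and the late mean (t6–t9) is 0.55, so early minus late = −0.40. The within-participant contrast in the 20 AS and AA participants has variance 0.55 × (1/4 + 1/4)/20 = 0.01375, so its standard error is 0.117.

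**Step 3: full GLS projection, t1–t9 fit**

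| Variances (inter/intra) | Drift per week | Bias of λ | SE of λ | 95% interval excludes 0 | Bias of μS − μA |
|---|---|---|---|---|---|
| 4.98/0.55 | 0.1 | −0.397 | 0.117 | 92% | +0.20 |
| 2.62/2.91 | 0.1 | −0.377 | 0.262 | 30% | +0.17 |
| 4.98/0.55 | 0.05 | −0.199 | 0.117 | 40% | +0.10 |
| 2.62/2.91 | 0.05 | −0.189 | 0.262 | 11% | +0.08 |

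The third column against Step 2 shows that 94% to 99% of the −0.40 contrast ends up in λ (0.377/0.40 and 0.397/0.40). Simulation with REML fits and the baseline covariate (3,000 runs per setting) gave 92.2% and 29.4% at 0.1 per week, 39% and 10% at 0.05, and 5.0% and 4.8% with no drift. Reversing the drift reverses the sign of λ at about the same rate.

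**Step 4: other settings at 0.1 per week**
- Table 2's interval limits for the variances: 57% (upper) and 99.6% (lower).
- The occasions in Section 10.3 (t1, t2, t6–t9): early minus late = 0 − 0.55 = −0.55. The fit gives −0.549 (rate 84%) and −0.538 (rate 25%) for the two variance settings.
- Section 10.3 also considers the case "when the sample size is reduced to 30 participants". There the t1–t9 rates are 81% and 22%.

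**Step 5: where the bias does not arise**
- A constant maintenance shift gives zero bias in λ.
- A drift of 0.1 that stops after the second maintenance week gives (0 + 0.1 + 0.1 + 0.1)/4 − 0.1 = −0.025 in the t1–t9 fit. In the Section 10.3 version, which sets t2 against t6–t9, it gives −0.10.
- The t1/t9 fit and the t1, t6–t9 fit, both with λ = 0, have zero bias in both treatment contrasts under common drift.

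**Step 6: add a week effect.** The bias in λ and in μS − μA becomes zero. The simulated rate is 5.3% (4.98/0.55) and 5.2% (2.62/2.91).

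**The case against.** The strongest reply is that this is an exploratory fit in a preliminary study. λ has no planned hypothesis test, so the rates above are chances that an exploratory interval excludes zero, not the type I error of a stated test. That stands, and it limits how serious the point is.

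The drift is also assumed. Section 2.2 says of the pilot trial "Results from this study were negative with a strong placebo effect", and a reader might infer that a placebo response will fade during maintenance. The documents do not support that: the same sentence goes on to describe the improvement under tACS and sham, relative to tDCS, as lasting. The pilot sham change of −2.29 in Table 2 is a single pre-to-post change and says nothing about weekly trend. Equally, nothing in the documents shows that scores stay flat from t2 to t9, which is what the model requires.

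Section 10.2 promises goodness-of-fit diagnostics, modified versions of the main analyses, and graphs of the data and fitted model. These might reveal a trend in SS and SA, but no week term is named and no action is tied to what the graphs show. This weakens the point without removing it.

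Finally, Section 10.3 itself warns: "Inclusion of the carryover effect in the model can reduce precision and power for the test of treatment effects". A week effect costs further precision for λ. That is true, but the smaller standard error is valid only if there is no drift.

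**Conclusion.** The point holds for the exploratory carryover analysis and should be fixed. As written, a shared change between t2–t5 and t6–t9 is estimated almost wholly as λ. At an assumed 0.1 unit per week with 40 participants, the bias in λ is about 0.4 AHRS unit and the bias in μS − μA from the same fit is about 0.17 to 0.20. The chance that λ's interval wrongly excludes zero is about 92% or 30%, depending on whether the intra-subject variance is 0.55 or 2.91. It falls to about 40% or 11% at half that drift and to the nominal 5% with none.

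A reader might infer that the trial's main result is compromised, or that any shared drift produces a false lasting benefit. Neither follows. The primary t1/t9 fit and the t1, t6–t9 sensitivity fit are unbiased under common drift, a constant maintenance shift does no harm, and falling scores would suggest lasting harm instead of benefit. The percentages are conditional on an assumed drift and are not a property of the plan alone.

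**What to change.** In Section 10.2, state that every fit containing λ will include a categorical effect for the maintenance occasions used. λ is then identified by the randomised contrast of AS and AA against SS and SA. Apply the same rule if the carryover model is used for alpha power in Aim 3, where EEG is recorded at t2, t4 and t9. In the same edit, reconcile the occasion sets given for the carryover fit in Sections 10.2 and 10.3, and recompute Figures 4 and 8 for the revised model.

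The cost is one sentence and, for t1–t9, seven extra fixed effects on 40 × 9 = 360 observations. The standard error of λ rises from 0.117 to 0.165 (from 0.262 to 0.360 with intra-subject variance 2.91), because the SS and SA change is now estimated: by hand, √(2 × 0.01375) = 0.166. The standard error of μS − μA hardly moves (0.255 to 0.261 with Table 2's components). The two fits with λ = 0 need no change.
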